Chief Investigator	[name] Arthritis Research UK Primary Care Centre Research Institute for Primary Care & Health Sciences [name] [contact] [contact]
Principal Investigator	[name] Arthritis Research UK Primary Care Centre Research Institute for Primary Care & Health Sciences [name] [contact] [contact]
Sponsor	[name] Head of Research Integrity, Directorate of Engagement & Partnerships, [name] [name] [contact]
Funder	[name]: NIHR Research Professorship (NIHR-RP-2014-04-026)
Study Management	Arthritis Research UK Primary Care Centre Research Institute for Primary Care & Health Sciences [name] [name] [contact]
Lead Statistician	[name] Senior Research Fellow: Epidemiology and Applied Statistics Arthritis Research UK Primary Care Centre Research Institute for Primary Care & Health Sciences [name] [contact] [contact]
Key Protocol Contributors	
 - [name], GP Partner & NIHR Academic Clinical Lecturer in General Practice - [name], Health Informatics Specialist Arthritis Research UK Primary Care Centre Research Institute for Primary Care & Health Sciences [name] [contact]

STUDY SUMMARY

Study title	Automated Check-in Data Collection Study	
Internal ref. number (or short title)	AC DC STUDY	
Study design	Pilot feasibility	
Study participants	Patients consulting in general practice, completing an automated check-in screen prior to their consultation.	
Planned sample size	Approximately n=1166 per participating general practice (depending on practice list size and number of consulting clinicians during recruitment period). Total sample size n=9604, ~11 general practices	
Planned recruitment period	3 weeks in each participating general practice.	
	Objectives	Outcome measures
Primary	To assess patient acceptability of answering two research questions in the general practice waiting room using an automated check-in screen.	Percentage of completed automated check-in screens with entered research data.

STUDY FLOW CHART

Flow chart demonstrating recruitment of participants into the study.

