5.5 Consent

Consent to participate in this study will be obtained, in line with the definition outlined in Article 4(11) of the GDPR guidance, “any freely given, specific, informed and unambiguous indication of the data subject’s wishes by which he or she, by a statement or by a clear affirmative action, signifies agreement to the processing of personal data relating to him or her”⁶. Consent to participate will therefore be implied by question completion. The study invitation poster and PIL (displayed alongside the automated check-in screen for the period of recruitment) will explain the purpose of the study, what is involved and what will happen to data that the participant supplies. No patient identifiable information will be collected. Completion of the research questions will be taken as consent to participate in the study.

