6 STATISTICS AND DATA ANALYSIS

6.1 Sample size calculation

The average list size of CRN WM general practices is 7,500 patients, of which approximately 6,000 (80%) will be 18 years of age or over. With the minimum required appointments, per week, per 1,000 patients being 72¹¹. Assuming the same rate of appointment use in those under and over 18 years, there will be an average of 432 appointments per week for those aged 18 years of age or over. Over three weeks therefore, discounting an approximate 10% of patients who have either; >1 appointment booked within the three-week period, lack capacity to complete the automated check-in screen, or the appointment is for either a telephone appointment or a home visit, the practices can expect approximately 1166 eligible participants.

One of the outcomes of this study is to estimate the proportion of people who are happy for their practice to contact them about any future research studies which are relevant to their health. Assuming that approximately 50% will respond positively to this question, 9604 people will need to respond to the question in order to estimate a 95% confidence interval for this proportion formally with a precision of 0.01. Assuming that 80% of those who use the automated check-in complete the additional questions, this would require approximately 12005 people to complete an on-screen check-in in order to achieve sufficient responders. This equates to approximately 11 practices displaying the questions for 3 weeks each, dependent on practice size and actual use of the automated check-in screens.

One AC DC participant check-in query log per practice, completed by practice administration staff, with regards to queries made as a result of the two additional research questions on the patient automated check-in screen, will allow the study team to assess the impact of check-in completion for general practice operationalisation.

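### Does the summary's planned sample size contradict itself, since 1,166 per practice over about 11 practices does not give 9,604?

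*Combined protocol and SAP*

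**What the plan says.** The planned sample size row of the study summary opens with "Approximately n=1166 per participating general practice", qualified by list size and the number of clinicians consulting, and ends with "Total sample size n=9604, ~11 general practices". Neither count carries a unit. The same table describes the participants as "Patients consulting in general practice, completing an automated check-in screen prior to their consultation".

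Section 6.1 (Sample size calculation) gives the derivation. From list size and appointment rates it concludes that "the practices can expect approximately 1166 eligible participants" over three weeks. Separately, for the contact question, it says that "9604 people will need to respond to the question in order to estimate a 95% confidence interval" with a precision of 0.01. Assuming 80% completion among people who use the screen, it adds that "this would require approximately 12005 people to complete an on-screen check-in in order to achieve sufficient responders". It converts this to about 11 practices, "dependent on practice size and actual use of the automated check-in screens".

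Section 5.5 (Consent) bears on who counts as a participant: "Completion of the research questions will be taken as consent to participate in the study".

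**The concern.** A per-practice number, a number of practices and a total in one row invite the reader to multiply. The product is 12,826, not 9,604. Working backwards, 9,604 over 11 practices is 873 each, and 9,604 at 1,166 each needs 8.2 practices. The approximate signs do not absorb the gap: even 10 practices would give 11,660.

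The summary does not say which unit applies. Its description of participants points to people who check in, section 5.5 points to people who answer, and section 6.1 attaches the word participants to the eligible patients. The distinction matters in this study, because the primary outcome is the percentage of check-ins with research data entered. Check-ins are its denominator, and people entering data are its numerator. If 9,604 were taken as the number of check-ins to collect, 80% completion would give 9,604 × 0.80 = 7,683 responders and a half-width of 1.96 × √(0.25 / 7,683) = 0.0112, short of the planned 0.01.

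**Working it through.** **Inputs, all from section 6.1:** average list size 7,500; 80% aged 18 or over; 72 appointments per week per 1,000 patients; three weeks; 10% discount; expected proportion 0.50; precision 0.01 at 95% confidence; 80% completion.

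**1. Eligible patients per practice**
- Adults: 7,500 × 0.80 = 6,000
- Appointments per week: 6 × 72 = 432
- Three weeks less 10%: 432 × 3 × 0.90 = 1,166.4, stated as 1,166. Reproduced.

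**2. Responders needed**
- n = 1.96² × p(1 − p) / d² = 3.8416 × 0.25 / 0.0001 = 9,604. Reproduced.

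**3. Check-ins needed**
- 9,604 / 0.80 = 12,005. Reproduced.

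**4. Practices needed**
- 12,005 / 1,166 = 10.3, rounded up to 11. Reproduced.

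**5. Where the 34% gap comes from**
- 12,826 / 9,604 = 1.34
- Completion factor: 1 / 0.80 = 1.25
- Rounding up to whole practices: 12,826 / 12,005 = 1.07
- 1.25 × 1.07 = 1.34, so these two steps account for the whole gap.

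**6. The row in a single unit**

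| Unit | Expected per practice | Expected from 11 practices | Required |
|---|---|---|---|
| Eligible patients, all taken as checking in on screen | 1,166 | 12,826 | 12,005 |
| Responders at 80% completion | 1,166 × 0.80 = 933 | 12,826 × 0.80 = 10,261 | 9,604 |

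In either unit, 11 practices meet the requirement.

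**7. Precision if the plan is followed**
- Half-width = 1.96 × √(0.25 / 10,261) = 0.0097, against a target of 0.01.

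**8. Could a misreading change the data?** Section 5.9 fixes recruitment at 21 consecutive days per practice, and the summary gives the same three weeks. No section closes recruitment when a count is reached. Someone who took 9,604 as check-ins would still have about 11 practices printed in the same row and would run each for three weeks. The result is the line in step 7. To arrive at 0.0112, one would have to disregard both the printed number of practices and section 6.1.

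**The case for a change.** The strongest case for a change is that a summary should be readable by itself and this row is not. It takes the first and last links of the calculation and omits what joins them, the 80% and the 12,005. A label would cost a few words. That criticism of the presentation stands. It does not make the unit unsettled in the protocol as a whole: section 6.1 states what 9,604 counts and gives the check-in requirement separately as 12,005, so reading 9,604 as check-ins contradicts the text. A total expressed in responders also fits the consent model in section 5.5.

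A second argument is that the step from 12,005 check-ins to 11 practices treats every eligible patient as a screen user without saying so, and leaves little slack. At 80% completion, 9,604 responders from 12,826 eligible patients requires 9,604 / (12,826 × 0.80) = 93.6% screen use. The arithmetic is right, but it concerns non-use beyond what is already removed, because the 10% discount in section 6.1 includes patients unable to complete the screen, along with telephone appointments and home visits. Section 3.1 requires all patients to check in on screen, and section 6.1 makes the number of practices conditional on actual use. The dependence is therefore acknowledged, though without a threshold.

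**Conclusion.** No change is needed. The row places an expected number of eligible patients per practice beside a required total of responders and labels neither, so it does not multiply out. That is a clerical slip in one summary cell. Section 6.1 defines both counts and connects them, and 1,166, 9,604, 12,005 and 11 all reproduce.

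The slip has no effect on the number of practices, the recruitment period, the data extracted or the analysis. About 10,261 responders and a half-width of 0.0097 are expected with or without a label. This rests on the plan's own inputs: the average list size, the appointment rate, the 10% discount, 80% completion, on-screen check-in by all eligible patients, and the simple binomial formula at a proportion of 0.50. If screen use or completion turns out lower, precision will be somewhat worse, but relabelling the row would not alter that.

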2 AIM & OBJECTIVES

The aim of this study is to examine patient acceptability, for providing brief research information, whilst self-completing an automated check-in screen prior to any general practice consultation.

Primary objective

The specific objectives of this study fall into two categories; research evaluation and process evaluation. By piloting the use of the automated check-in screen to collect additional research data, the answers to these objectives will then provide feasibility information on the future use of the automated check-in screens for the identification of potentially eligible participants that would be happy to be contacted about future research studies relevant to their health and with information on patient acceptability of answering simple research questions, within the general practice waiting room.

Research evaluation objectives:

1. To examine completion rates of the two additional research questions on the automated check-in screen.
2. To estimate the number of patients that would be happy to be contacted about future research studies relevant to their health.
3. To estimate the number of patients reporting degrees of pain and which severities of pain.
4. To explore any demographic variances in completion responses.
5. To estimate research question completion rate feasibility, for future use of automated check-in screens in the collection of research data.

Process evaluation objectives;

1. To assess patient acceptability of answering an additional two research questions within the waiting room, whilst completing an automated check-in screen.
2. To explore research question completion rates depending on the time differences between; check-in completion, booked appointment time and actual consultation time.
3. To assess the impact of check-in completion for general practice operationalisation.
4. To describe the quantity and detail of any participant queries, made as a result of asking two additional research questions on the patient automated check-in screen.

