3.1 Study population

All patients of age 18 and over, who can read and respond in English and with a booked appointment, consulting with any Health Care Professional (HCP) at their general practice, during the recruitment period will be eligible to participate. All patients are required to confirm their attendance at the general practice by using the automated check-in screen. If the patient completing the automated check-in screen is 18 years of age or over, the additional research questions will appear for completion. The additional research questions will not appear on any subsequent appointment check-in screen during the recruitment period, for those participants who have already completed the questions.

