5.3 Screening

The two research questions will not appear for patients checking-in for a booked appointment who are under the age of 18 years or for those that have already answered the research questions during the recruitment period.

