5.6 Data collection

A pseudonymised data extraction, for all booked appointments scheduled and attended during the three-week recruitment period at each participating practice, for those patients of age 18 years or older, will be downloaded. Data to be included in the download will include; patient demographic data (gender and age), date and times (of patient check-in, booked appointment and consultation), check-in ID (system user / practice) and self-reported answers to the two research questions. These items will form the basis of the quantitative data collection, see Table 1 for data items and from where the quantitative data will be collected.

For each participating practice, metadata to include; practice list size, demographic data (gender and age), deprivation score and total number of practice based consultations booked over the three-week recruitment period, will also be collected at aggregate level.

Participant data provided in terms of check-in queries, made as a result of the two additional research questions on the patient automated check-in screen will be anonymously logged by practice administration staff, to assess the impact of check-in completion for general practice operationalisation. The log of queries will be populated for a total of 4 weeks. Three weeks, during recruitment to the study and for one week following the end of recruitment.

Automated check-in data collection

Patients will be asked to complete two self-report research questions during automated check-in for a booked appointment at their general practice. The data entered will be appended to their electronic medical record and pseudonymised data will be downloaded, for all patients for whom the research questions appeared. This data will consist of unique study identifiers, gender, age, times (check-in, booked and consultation), check-in ID (system user / practice) and the study research coded entries.

Table 1: Data items and method of data collection

Data items	Description	Method of data collection
Patient demographics	Gender	EMIS data extraction
	Age	
Date and time of:	Check-in	
	Booked appointment	
	Consultation	
Check-in ID	Dichotomous: 'System user' or 'Practice'	Patient self-reported
Degree of bodily pain experienced during the past 4 weeks.	Single question: 1-6 point scale – degree of pain	
Consent to contact about future research studies of relevance.	Dichotomous: Yes or No	

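### The primary outcome counts completed check-in screens, so later check-ins by patients who have already answered, where the questions are hidden, lower the completion rate although nothing was asked

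*Combined protocol and SAP*

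**What the plan says.** The only definition of the primary outcome is in the study summary table: "Percentage of completed automated check-in screens with entered research data". The unit is the screen.

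Section 3.1 says that the questions "will not appear on any subsequent appointment check-in screen during the recruitment period, for those participants who have already completed the questions". Section 5.3 repeats the rule: they are not shown "for those that have already answered the research questions during the recruitment period".

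Repeat attendance is foreseen. Section 6.1 takes off about 10% for several reasons together, one of which is ">1 appointment booked within the three-week period".

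Other places lean towards the patient or the question as the unit. Research objective 1 in section 2 is "To examine completion rates of the two additional research questions on the automated check-in screen". Section 6.1 plans on people: "Assuming that 80% of those who use the automated check-in complete the additional questions". Section 6.2 compares responders with non-responders. None of these sets a denominator.

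Section 5.6 describes the data twice. It opens with "A pseudonymised data extraction, for all booked appointments scheduled and attended during the three-week recruitment period at each participating practice", restricted to adults, and the items it then lists do not include an identifier. Further down it describes a download limited to patients who were shown the questions, and there it does name a unique study identifier. Table 1 does not list one.

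**The concern.** The stated objective is acceptability: do patients answer when asked? A check-in at which the questions are suppressed by design says nothing about that, yet it is a completed check-in screen with no research data entered. Under the summary's wording it counts as a failure. The resulting rate would mix willingness to answer with how often willing patients come back within three weeks. Practices with more frequent attenders would look less accepting for that reason alone.

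At stake is the headline figure. Research objective 5 uses the completion rate to judge future use of the screens for collecting research data. The responder versus non-responder comparisons in section 6.2 are exposed too, because in an appointment-level file one patient could appear in both groups.

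**Working it through.** **Inputs.** From section 6.1: completion p = 0.80 among people using the kiosk. Not in the documents, so assumed: r, the share of kiosk check-ins that are repeats; and q, the chance that a patient who did not answer does so when shown the questions again, taken from 0 to 0.80. Also assumed: at most one repeat per patient, and repeats independent of answering (relaxed in step 4).

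**1. The plan's own figures.**
- Responders: 1.96² × 0.5 × 0.5 / 0.01² = 9604.
- People checking in: 9604 / 0.80 = 12005.
- Per practice: 6 × 72 × 3 × 0.9 = 1166.4, stated as 1166.
- Practices: 12005 / 1166 = 10.3, so 11.

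All reproduce, and all count people. The sample size is therefore not affected by this point.

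**2. The outcome as worded.** A share 1 − r of screens are first check-ins, completed with probability p. Of the repeats, a share p come from earlier answerers and carry no data. The other 1 − p are answered with probability q.

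Rate = (1 − r)p + r(1 − p)q

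Shortfall from p = r[p − (1 − p)q]

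The bracket is 0.80 at q = 0 and 0.80 − 0.20 × 0.80 = 0.64 at q = 0.80. Each 1% of repeats therefore costs 0.64 to 0.80 points. Illustrative repeat shares:

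| r | q = 0 | q = 0.80 |
|---|---|---|
| 2% | 78.4% | 78.7% |
| 5% | 76.0% | 76.8% |
| 10% | 72.0% | 73.6% |

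For other values of p, with q from 0 to p, the cost per 1% of repeats is 0.36 to 0.60 points at p = 0.6 and 0.81 to 0.90 at p = 0.9.

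**3. How much of this is suppression.** At r = 0.10, the screens on which the questions were displayed are 0.90 + 0.10 × 0.20 = 0.92 of the total. Per displayed screen the rate is 0.720 / 0.92 = 78.3% at q = 0 and 0.736 / 0.92 = 80.0% at q = 0.80. Suppressed screens thus account for 78.3 − 72.0 = 6.3 of the 8.0-point shortfall at q = 0, and for all 6.4 points at q = 0.80. The remaining 1.7 points at q = 0 come from questions that were shown again and not answered.

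**4. Without independence.** Let a be the answerers' share of repeats. The shortfall becomes r[p − (1 − a)q]. At p = 0.80 and q from 0 to 0.80, the bracket runs from 0 (a = 0, q = 0.80) to 0.80 (a = 1, or q = 0). So 0.64 is a floor only under independence.

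**5. Scale.** The simple 95% half-width for 80% of 12005, ignoring clustering by practice, is 1.96 × √(0.8 × 0.2 / 12005) = 0.0072, about 0.7 points. Under the assumptions of step 2, a 1-point shortfall needs repeats of only 0.01 / 0.80 = 1.25% to 0.01 / 0.64 = 1.56% of kiosk check-ins.

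**The case against.** The strongest reply is that one cell of a summary table is being read apart from the design. Section 5.3 screens earlier answerers out together with under-18s. Section 5.6 describes a download for patients who were shown the questions. Section 6.1 applies its 80% to people, and section 6.2 promises a SAP before recruitment ends, the usual home for a denominator rule. This shows that a patient-level analysis was probably intended, but it does not supply the rule. Section 3.1 itself calls the question-free screen a check-in screen, and the restriction in section 5.6 is on patients: an earlier answerer was shown the questions, so the later check-ins stay in.

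Three limits on the point do stand.

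- **Direction.** A reader might infer that the per-screen rate is always too low. That is certain for suppressed screens, which add only to the denominator. Showing the questions again to patients who did not answer can add completions. Under independence the net shortfall turns negative when q exceeds p/(1 − p), which requires p below 0.5. The documents also do not say how coded answers attach to appointment rows. If they attach by patient, a later row could show data that were not entered at that check-in, which would be a different error and not a remedy.
- **Linkage.** A reader might infer from the first item list in section 5.6 and from Table 1 that repeat check-ins cannot be linked. The documents do not support that: the same section names a unique study identifier, and both descriptions may refer to one download.
- **Size.** It is tempting to treat the 10% in section 6.1 as the repeat share. It pools repeats with lack of capacity, telephone appointments and home visits, so it is neither an estimate nor a bound.

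It is also fair to say that a displayed-screen denominator would remove the suppression problem. The choice between sensible denominators matters less: at r = 10%, the displayed-screen rate is 0 to 1.7 points below the first-display 80%. The ever-answered rate, p + (1 − p)q × r/(1 − r), is 0 to 1.8 points above it.

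**Conclusion.** The point holds. The primary outcome as worded counts screens on which nothing was asked as screens without data, and no section takes them out. Suppressed screens can only lower the rate. The size is illustrative because the repeat share is not given: 0.64 to 0.80 points per 1% of repeats with 80% completion at first display, at most one repeat per patient and repeats independent of answering, or 0 to 0.80 if repeats depend on answering.

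A reader might infer that the study could reach a wrong decision. The documents do not support that: the study is descriptive and sets no completion threshold. The harm is a misreported headline rate. It is worth correcting before extraction because the correction is cheap and the denominator would otherwise be chosen with the data in view.

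**What to change.** In the study summary, and in section 6.2 or the SAP:

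- Define the primary outcome per patient. Denominator: each adult's first kiosk check-in in the 21-day window at which the questions were due to appear. Numerator: those answering at that check-in.
- State whether one answer is enough or both are needed. Section 5.4 allows the first question to be answered and the second skipped or timed out.
- Exclude later check-ins of earlier answerers. Report the ever-answered rate and the rate per displayed screen as secondary.

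In section 5.6, reconcile the two descriptions of the extraction, confirm that the unique study identifier already named there is in the appointment-level file, and add it to Table 1. This is a consistency check. The day-3 export in section 8.2 could be used for it, ahead of the extraction on or after day 28 (section 5.9).

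The cost is wording and one de-duplication step. The planned numbers do not change.
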